We have carefully considered but decided against proposing a prospective cohort study of the predictive accuracy of risk assessment tools because this design would have an insurmountable flaw if undertaken alongside current NHS practice. The fundamental aim of risk assessment is to predict patients whose VTE will be prevented by prophylaxis. Over 70% of medical patients in the UK receive prophylaxis when the Department of Health risk assessment tool has been used (NICE 2018). In this situation, around half of the VTE that could have been prevented by prophylaxis will have been prevented and the prognostic model will largely be predicting VTE that were not prevented by currently-used prophylaxis. Any prognostic model derived in this setting would therefore be based on factors that predict non-preventable VTE whilst under-estimating (or missing) those that predict preventable VTE. A risk assessment tool that predicted non-preventable VTE while failing to predict preventable VTE would potentially be worse than useless.

In accordance with the commissioning brief, we propose and provide justification for an alternative efficient study design to estimate the cost-effectiveness of VTE risk assessment tools for hospital inpatients. We will use decision-analysis modelling of published evidence to determine how the cost-effectiveness of prophylaxis varies for different thresholds of risk.

This will determine whether risk assessment has the potential to be cost-effective compared with prophylaxis for all and, if so, what threshold of risk should be used for providing prophylaxis and what trade-off between sensitivity and specificity would be optimal for a risk assessment tool. We used this approach in our evaluation of risk assessment tools for prophylaxis for people with lower limb immobilisation due to injury (HTA15/187/06), showing that a risk assessment tool with sensitivity around 90% and specificity around 50% would be optimal, assuming an appropriate trade-off on the receiver operating characteristic (ROC) curve.

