The primary studies had important limitations and were generally judged as low quality. Reporting of the use of prophylaxis was variable and, where reported, it appeared that a substantial proportion of the study population had received prophylaxis. Many of the limitations, including inability to control for the use of prophylaxis, are not readily remediable. This suggests that, although further studies of risk assessment tools are in progress, they are unlikely to provide robust evidence to guide decision-making.

We identified one previous study that used decision-analysis modelling to estimate a risk threshold for prophylaxis in hospitalised medical patients (Le 2017). Undertaken from a United States health system perspective with a willingness to pay threshold of \$100,000 per quality-adjusted life year (QALY) gained, the analysis showed that prophylaxis was cost-effective for an average medical patient with a VTE risk exceeding 1.0%. This model has a number of similarities to our model of VTE risk assessment in lower limb immobilisation but also some key differences (other than the population studied), and to inform NHS practice modelling would need to be undertaken from a NHS perspective using NICE thresholds. However, it shows how decision-analysis modelling can be used to guide selection of an appropriate risk assessment tool and thus guide practice.

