The feasibility study will also determine whether standardised risk-assessment data can be prospectively recorded and collected in an efficient manner along with data showing whether prophylaxis is prescribed and administered. This is not essential to a fully pragmatic implementation study but would provide very valuable insights into the process of implementing risk-based VTE prophylaxis and would allow evaluation of alternative risk-assessment strategies. It will also allow us to determine the proportion of patients who would receive VTE prophylaxis with different risk-assessment tools, and will thus inform the modelling and the design of any future implementation study. Feasibility work will include estimating user acceptability and clinician time involved in risk-assessment.

We will use the following definitions of the health technology, study population, setting and outcomes across both elements of the study.

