Data will be extracted independently by one reviewer using a standardised data extraction form and independently checked for accuracy by a second. Uncertainties will be resolved by discussion. Those that cannot be resolved will be referred to the rest of the project team. Where multiple publications of the same study are identified, data will be extracted and reported as a single study. The following standardised data will be extracted from each eligible study: date, setting, population characteristics (age, sex, diagnosis), risk-assessment tool characteristics, VTE outcome definitions and results according to risk strata. If appropriate, the authors of the primary studies will be contacted for missing data.

Methodological quality will be assessed using a generic list of features recommended by Altman (Altman 2001) and Moons (Moons 2014) for prediction modelling studies and used in HTA15/187/06.

Limitations in the data available and marked heterogeneity between primary studies identified in our scoping review mean that meta-analysis is unlikely to be possible. We therefore plan to present descriptive estimates of key parameters from each study. If adequate data are identified, we will draw upon extensive experience from previous projects to undertake appropriate meta-analysis.

Literature searches for key parameters in the model will be developed as the project progresses, in response to the needs of the model. We anticipate that many of the parameters required will be similar to those used to populate our existing model on the cost-effectiveness of VTE prophylaxis for people with lower limb immobilisation due to injury (HTA15/187/06) and therefore literature searches will focus on updating reviews conducted to inform our previous model and replacing any data sources that are specific to patients with lower limb injury and not generalizable to hospital inpatients.

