We will use existing literature to estimate the risks of VTE and bleeding outcomes (as defined above) for the cohort if no prophylaxis is given and then use relative risk estimates from existing systematic reviews of VTE prophylaxis for relevant inpatient populations to estimate the VTE and bleeding risks with prophylaxis (NICE 2018, Kahn 2018). Alternatively, if more reliable event rate estimates are available for inpatients receiving prophylaxis, we will use the inverse of the relative risks to estimate the risks in those not receiving prophylaxis. We will explore using different risk estimates for different inpatient populations, depending upon the data available.

The proportion of patients having VTE prophylaxis for each strategy is determined by the risk of VTE in the population and the sensitivity and specificity of the strategy for identifying patients who go on to have VTE. The proportion having VTE and / or bleeding events is then calculated for those receiving or not receiving prophylaxis which is dependent on the factors above plus the effectiveness and safety of prophylaxis. In the secondary analysis the risk of bleeding events will also depend upon the sensitivity and specificity of the IMPROVE bleeding risk score for predicting bleeding events.

The sensitivity and specificity of each risk-assessment tool for predicting VTE will be estimated using data from the systematic review, with the clinical expert group being used to judge the appropriateness of estimates and select between studies if more than one estimate exists for any tool.

We will also undertake the following threshold analyses:

- 1. Theoretical risk-assessment tools will be examined with sensitivity and specificity varying across a credible ROC curve, to determine the balance of sensitivity and specificity at which effectiveness (QALYs) and cost-effectiveness (net benefit assuming willingness to pay £20,000/QALY or £30,000/QALY) is optimised
- 2. A one-way sensitivity analysis will vary the baseline risk of VTE in a comparison between prophylaxis for all and prophylaxis for none, to determine the thresholds of baseline risk at which prophylaxis for all is more effective and cost-effective than prophylaxis for none (i.e. the threshold at which the benefits of prophylaxis outweigh the risks and the threshold at which the benefits outweigh the risks and costs)

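### Tool sensitivity is taken from substantially treated cohorts with no adjustment for prophylaxis, and prophylaxis use is not on the extraction list

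*Protocol*

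**What the plan says.** Protocol section 4.2 makes the share of patients treated under each strategy, and hence the events prevented, depend on the untreated VTE risk and on "the sensitivity and specificity of the strategy for identifying patients who go on to have VTE". For the tools, "The sensitivity and specificity of each risk-assessment tool for predicting VTE will be estimated using data from the systematic review". The only safeguard named there is a review by clinicians, who also choose between studies where a tool has more than one estimate. No adjustment for prophylaxis in the source cohorts is named.

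Baseline risk is handled differently. If event rates in patients on prophylaxis are the more reliable source, "we will use the inverse of the relative risks to estimate the risks in those not receiving prophylaxis".

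Section 1.0 (Existing literature) reports that recording of prophylaxis in the source studies was variable and that, where reported, "it appeared that a substantial proportion of the study population had received prophylaxis". The extraction list in section 4.1 covers date, setting, population characteristics, "risk-assessment tool characteristics, VTE outcome definitions and results according to risk strata". Prophylaxis use is not on it.

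Section 1.0 (Background and Rationale) rejects a new cohort study because a model derived under prophylaxis would end up "under-estimating (or missing) those that predict preventable VTE".

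Section 3.1 says the feasibility study will show "the proportion of patients who would receive VTE prophylaxis with different risk-assessment tools, and will thus inform the modelling". The Summary of Research and section 9.0 place modelling in Year 1 and pilot data collection in Year 2.

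**The concern.** The protocol argues that accuracy measured under prophylaxis is distorted and uses this to rule out new primary data. It then feeds the model accuracy estimates from cohorts with the same limitation, as section 16.1 concedes. One model input has a conversion from treated to untreated patients and the other has none.

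If prophylaxis followed risk in those cohorts, events in tool-positive patients were prevented more often than events in tool-negative patients, so the observed share of events that were tool-positive falls. The model applies that lowered sensitivity to an untreated population. The proportion treated hardly changes, because at a low VTE risk it is close to one minus specificity. The tool strategy therefore keeps its costs and bleeding but loses part of its benefit, against prophylaxis for none as well as prophylaxis for all.

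This matters because section 16.1 intends the results to inform whether about 70% or about 40% of inpatients should receive prophylaxis, and section 8.0 directs them to NICE.

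**Working it through.** The protocol gives no figure for this effect, so there is none to reproduce.

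**Inputs.** True sensitivity s, relative risk RR of VTE on prophylaxis, and prophylaxis coverage cH in tool-positive and cL in tool-negative patients. None of these is in the protocol for the source cohorts; all values below are assumptions. The nearest figure is over 70% of UK medical patients treated when the Department of Health tool is used (section 1.0), which is an overall share, not one by stratum.

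**Formula.** Events in a stratum with coverage c are reduced by the factor 1 − c(1 − RR), so

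observed sensitivity = s[1 − cH(1 − RR)] / {s[1 − cH(1 − RR)] + (1 − s)[1 − cL(1 − RR)]}.

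**Results with s = 0.80.**

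| cH / cL | RR | Calculation | Observed sensitivity |
|---|---|---|---|
| 90% / 30% | 0.5 | 0.44 / (0.44 + 0.17) | 72.1% |
| 90% / 30% | 0.4 | 0.368 / (0.368 + 0.164) | 69.2% |
| 90% / 30% | 0.6 | 0.512 / (0.512 + 0.176) | 74.4% |
| 80% / 50% | 0.5 | 0.48 / (0.48 + 0.15) | 76.2% |
| 70% / 70% | 0.5 | 0.52 / (0.52 + 0.13) | 80.0% |
| 30% / 90% | 0.5 | 0.68 / (0.68 + 0.11) | 86.1% |

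The last two rows show that equal coverage gives no bias and that reversed coverage favours the tool.

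**Effect on the model.** The share of VTE falling in tool-negative patients is truly 20%. In the first four rows it would be read as 27.9%, 30.8%, 25.6% and 23.8%, overstated by about 39%, 54%, 28% and 19%. Total VTE is a milder measure. Under the tool strategy it is 1 − s(1 − RR) of the untreated level. At RR 0.5 and 90%/30% this goes from 1 − 0.80 × 0.5 = 60% to 1 − 0.721 × 0.5 = 64%, about 7% relative (0.64/0.60). The tool's gain over prophylaxis for none falls from 40 to 36 points, and its shortfall against prophylaxis for all (50% of the untreated level) grows from 10 to 14 points.

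**Specificity.** With untreated risk 1% and true sensitivity/specificity of 90%/50% or 70%/60%, specificity moved by at most 0.3 points, so the issue is essentially one of sensitivity.

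**Does a correction work?** Dividing each stratum's events by its own factor gives, in the first row, 0.44/0.55 = 0.80 and 0.17/0.85 = 0.20, hence 0.80/(0.80 + 0.20) = 80%. The true value is recovered exactly, provided cH, cL and RR are known.

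**Inverse relative risk.** Dividing by RR is the special case c = 1. For a cohort with coverage c the divisor is 1 − c(1 − RR). With c = 0.7 and RR = 0.5 that is 0.65, so using 0.5 instead would overstate untreated risk by 0.65/0.5 = 1.30.

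**The case against.** The protocol does not hide the problem. Sections 1.0 and 16.1 state it. Tools are to be selected partly on study quality, experts judge the estimates, elicitation and scenario analyses are considered where data are minimal, and uncertainty in predictive accuracy will be explored. The theoretical-tool analysis does not rest on any one tool's published sensitivity, and the comparison of prophylaxis for all with prophylaxis for none uses no sensitivity at all. These points stand, and they limit the damage. None is a correction, however. A probabilistic sensitivity analysis centred on an uncorrected estimate does not move its centre. The theoretical ROC curve may draw on the same cohorts, and section 16.1 then asks which existing tools operate near the optimum, which needs their published sensitivities.

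Three stronger readings are tempting and are not supported:

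- A reader might infer that the model is biased against risk assessment outright. The direction depends on coverage by risk stratum, which the protocol does not give.
- A reader might infer that the omission from the extraction list makes correction impossible. Section 4.1 extracts results by stratum, allows authors to be contacted for missing data, and uses quality checklists whose items are not shown and may cover prophylaxis. The accurate statement is that no correction is planned.
- A reader might infer that the inverse relative risk will be misapplied to partly treated cohorts. Section 4.2 ties it to patients receiving prophylaxis, for whom it is right. The 1.30 factor above shows only why the limit should be written down.

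It is also fair to say that coverage by stratum will often be unreported, so a corrected base case built on assumed coverage would be open to dispute. The fix allows for this.

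**Conclusion.** The concern holds in conditional form. The protocol uses sensitivities from substantially treated cohorts without adjustment and does not plan to extract the item needed to adjust them. Sensitivity is understated where tool-positive patients were treated more often, which is the likely pattern under risk-targeted prophylaxis but is undocumented. Under the assumed inputs the loss is about 4 to 11 percentage points from a true 80%. Without coverage by stratum the team cannot tell the size or the direction for any tool. The illustration assumes one RR in both strata and, within each stratum, treatment unrelated to risk.

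The timing conflict needs no assumption: pilot data collected in Year 2 are said to inform modelling scheduled for Year 1, and no re-run is scheduled.

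**What to change.** 1. Section 4.1: add prophylaxis use by risk stratum to the extraction list, and ask authors for it where unreported.
2. Section 4.2: where it is available, divide the events in each stratum by 1 − c(1 − RR) before computing sensitivity and specificity, and report corrected and uncorrected results.
3. Where it is unavailable, keep the published estimate in the base case and add a scenario over a stated coverage range that includes equal coverage.
4. State that the inverse relative risk applies only to event rates in fully treated patients, and use 1 − c(1 − RR) as the divisor for any mixed cohort.
5. Reconcile section 3.1 with the timetable, for example by one scenario re-run after the pilot using the proportion tool-positive. That informs specificity and the share treated, not sensitivity. It should be restricted to patients without a bleeding-risk exclusion, because the primary model leaves those patients out while section 5.1 does not.

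The cost is one extraction field, some author queries, one formula using a relative risk already planned for the model, and one re-run. The downsides are the constant-RR and within-stratum assumptions, and that many sources will support only the scenario range.

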At the end of phase 1 of the model each patient will be characterised according to whether or not they have suffered VTE or bleeding events. They will then enter phase 2 of the model, which will determine the lifetime costs and QALYs accrued by each patient. This phase will incorporate any long term consequences of both VTE and major bleeds.

Each patient in the cohort will accrue costs and outcomes determined by whether they receive prophylaxis or not, whether they developed clinically significant VTE, and whether they suffer any bleeding events. We will use parameter estimates and a model structure developed for our recent study of the cost-effectiveness of VTE prophylaxis for lower limb immobilisation due to injury (HTA15/187/06).

The total costs and QALYs accrued across the cohort will be calculated and a fully incremental analysis will be undertaken. Costs will be evaluated from an NHS and personal social services perspective. Future costs and benefits will be discounted at 3.5% in line with current best practice, as defined by NICE (NICE 2013).

Uncertainty about parameters that are subjected to formal evidence synthesis will be characterised by drawing samples from their appropriate joint posterior distributions. For parameters where the studies yield no or minimal relevant information with which to populate the model, elicitation sessions with experts, and scenario analyses will be considered. These sources of evidence will be combined to produce estimates of model parameters and define the associated probability distributions.

Differences in resource use between the different VTE prophylaxis strategies, including medications, clinical time to implement risk assessment, and management of VTE and bleeding-related adverse events, will be valued by applying Department of Health reference costs (Department of Health 2014) or PSSRU unit costs (Curtis 2015) for episodes of care and BNF list prices for medications (British National Formulary 2016).

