Analyses will be undertaken to identify the key parameters determining the costeffectiveness of the different strategies with the objective of identifying how secure the conclusions of the economic analyses are, given the available evidence. Uncertainty with respect to model parameters will be explored with a probabilistic sensitivity analysis (PSA). The information derived from PSA will be summarised graphically (within a costeffectiveness acceptability curve). The probability that the cost-effectiveness of the intervention is within the £20,000-£30,000 per QALY range, reflecting the thresholds typically used by NICE (NICE, 2013) in appraising health technologies will be explicitly reported.

If there is evidence that the tools perform differently in different subgroups, then we would explore this in the economic model to determine whether these differences translated into different estimates of cost-effectiveness.

The decision analytic model will be used to estimate the value of information of further primary research and determine the optimal direction of future research, whilst taking into account restrictions placed on potential research by widespread use of VTE prophylaxis. The

expected value of partial perfect information (EVPPI) will be estimated for groups of parameters. This will be done using the Sheffield Accelerated Value of Information application which calculates EVPPI directly from the PSA results avoiding the need for computationally expensive nested double loop simulations (Strong 2014). If the EVPPI estimates suggest that further primary research may be valuable to reduce the uncertainty around specific groups of parameters, then expected value of sample information (EVSI) analysis will be performed to inform decisions regarding future primary research (Strong 2015).

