We will use the decision-analysis model to (1) explore the potential impact of uncertainty in estimates of predictive accuracy, (2) identify the optimal balance of sensitivity and specificity for a risk-assessment tool, and (3) identify the appropriate risk threshold for providing prophylaxis. The first objective can be undertaken with limited data and the latter two by using theoretical risk-assessment tools with varying prognostic performance. These analyses will help to inform discussions reported in the NICE guideline as to whether 70% of inpatients receiving prophylaxis according to the Department of Health tool or the estimated 40% with the IMPROVE tool is more appropriate. We will also be able to determine which existing risk-assessment tools appear to operate at thresholds for performance likely to be optimal according to our model and, for risk-assessment scores, which score appears to provide an optimal threshold.

The model can therefore provide evidence to indicate whether more liberal or restrictive use of prophylaxis is likely to be appropriate. Ultimately, however, primary research will be required to determine the impact of a risk-adjustment tool (or tools) in practice, hence our concurrent plan to determine the feasibility of efficient methods to evaluate alternative approaches to the use of VTE prophylaxis.

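### If pooling proves impossible, as the protocol expects, nothing carries disagreement between studies of the same tool into the probabilistic analysis or the EVPPI for tool accuracy

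*Protocol*

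**What the plan says.** Protocol section 4.2 takes each tool's sensitivity and specificity from the systematic review. The clinical expert group judges whether the estimates are appropriate and is to "select between studies if more than one estimate exists for any tool". The same group sees the review outputs when choosing which tools to model. No step hides accuracy results while studies are chosen.

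Section 4.1 states that data limitations and "marked heterogeneity between primary studies identified in our scoping review mean that meta-analysis is unlikely to be possible", and plans descriptive estimates study by study. It leaves one door open: "If adequate data are identified, we will draw upon extensive experience from previous projects to undertake appropriate meta-analysis".

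For the PSA, section 4.2 describes two kinds of input:
- Inputs that went through a formal synthesis are sampled from their joint posteriors.
- Inputs with little or no evidence behind them get a different treatment, offered only as a possibility: "For parameters where the studies yield no or minimal relevant information with which to populate the model, elicitation sessions with experts, and scenario analyses".

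The value-of-information software named in section 4.2 "calculates EVPPI directly from the PSA results".

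Two other statements bear on accuracy. Section 4.2 says "Theoretical risk-assessment tools will be examined with sensitivity and specificity varying across a credible ROC curve". Section 16.1 says the model will "explore the potential impact of uncertainty in estimates of predictive accuracy", without giving a method.

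**The concern.** A tool with several conflicting studies and no meta-analysis fits neither kind of PSA input. It has not been formally synthesised, and its evidence is not absent or minimal. The only instruction that applies is to choose between the studies. Unless something is added, the spread entering the PSA is the chosen study's own sampling error, and disagreement with the other eligible studies is left out. EVPPI is computed from the same draws, so variance missing from the PSA is missing there too.

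Objective 3 in section 2.0 is to identify the key uncertainties and the value of reducing them, and section 8.0 lists value of information as a main output. Section 16.1 says the team shares the funding board's concern about the quality of predictive accuracy data. The acceptability curve and overall EVPI use the same draws, so the effect is not confined to EVPPI for accuracy. Choosing with results in view also lets the choice of study move the point estimate, and no criterion set in advance limits that.

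**Working it through.** The protocol states no accuracy variance, between-study variance or EVPPI, so there is no figure to reproduce. The check has three parts.

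**1. Routes into the PSA**

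| Situation for a tool | Route given in section 4.2 | Between-study spread carried? |
|---|---|---|
| Studies pooled | Joint posterior samples | Yes, if the model has random effects and the predictive distribution is used |
| No or minimal evidence | Elicitation or scenarios, to be considered | Possibly |
| Several conflicting studies, not pooled (expected under section 4.1) | Experts select between studies | No route stated |

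**2. When one study is too narrow**

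All inputs here are assumed. Take sensitivity 0.70 and 100 VTE events per study. On the logit scale the sampling SE is s = 1/√(100 × 0.70 × 0.30) = 0.218, a 95% range of 0.60 to 0.78. With k equal-sized studies and between-study SD τ, the variance for a new setting is τ² + (τ² + s²)/k. For k = 3:

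| τ | Predictive SD | 95% range | Predictive SD ÷ s |
|---|---|---|---|
| 0 | √(0.0476/3) = 0.126 | 0.65 to 0.75 | 0.58 |
| 0.3 | √(0.090 + 0.1376/3) = 0.369 | 0.53 to 0.83 | 1.7 |
| 0.5 | √(0.250 + 0.2976/3) = 0.591 | 0.42 to 0.88 | 2.7 |
| 1.0 | √(1.000 + 1.0476/3) = 1.162 | 0.19 to 0.96 | 5.3 |

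Setting the two variances equal, the single study is the narrower only if τ > s√((k−1)/(k+1)). For k = 3 and 100 events that is τ > 0.218 × 0.707 = 0.15. For studies of 500 patients with 1.5% events (7.5 events), s = 1/√(7.5 × 0.21) = 0.80, and the break-even rises to τ = 0.56. The direction therefore depends on both study size and disagreement.

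**3. Effect on net benefit and EVPPI**

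An illustrative simulation took a tool's net benefit as proportional to p·sens − pt·[p·sens + (1 − p)(1 − spec)]. The comparators were prophylaxis for all (p − pt) and for none (0). EVPPI for (sens, spec) is E[max NB] − max E[NB], with all else fixed. The threshold risk pt = 1.0% is borrowed from the US model described in section 1.0. The remaining inputs are assumed:
- 3 or 6 studies per tool, of 500 to 8000 patients, with about 1.5% events;
- sensitivity/specificity of 0.70/0.55 or 0.85/0.35, with logit correlation −0.6;
- baseline risk p of 0.6%, 1.0%, 1.5% or 2.0%;
- τ treated as known, and 300 replicates per cell.

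One randomly chosen study was compared with the random-effects predictive distribution:

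| τ | Median SD ratio, single ÷ predictive | Replicates in which single-study EVPPI is larger |
|---|---|---|
| 0.9 | 0.25 to 0.56 | 1 to 26% |
| 0.6 | 0.35 to 0.79 | 3 to 36% |
| 0.3 | 0.64 to 1.61 | 7 to 73% |
| 0 | 1.6 to 2.7 | larger on average wherever it is not near zero |

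The ratio of mean EVPPIs runs from about 0.06 (2.38/36.72) to 0.70 (9.11/13.06) at τ = 0.9. At τ = 0.6 it runs from 0.15 (1.77/11.54) to 1.71 (6.15/3.60), exceeding 1 only where p equals pt.

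**The case against.** A reader might infer that the plan certainly removes heterogeneity and that EVPPI for accuracy must come out too small. The documents do not support that, for these reasons:

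- **Pooling stays open.** Section 4.1 allows meta-analysis if the data are adequate, and section 4.2 would then sample from joint posteriors. This stands. The gap exists only if pooling fails, which is what the protocol expects.
- **Within-tool disagreement is not documented.** The heterogeneity is reported between primary studies generally. Section 1.0 attributes it to populations, methods and outcomes across many tools. Some of that spread may be irrelevant to the NHS decision, and counting all of it would overstate uncertainty. This also stands, and it is why exclusion for quality and applicability should be kept.
- **The direction is not fixed.** A small chosen study can carry more variance than a pooled result, and selection moves the mean relative to the decision boundary. The calculation confirms this.
- **Research may not be steered away from accuracy.** Sections 1.0 and 16.1 already reject a new prospective accuracy study on design grounds, so the recommendation against one does not hinge on EVPPI. The acceptability curve, overall EVPI and ranking of parameters are still affected.
- **Detail may sit in a later analysis plan.** Exact distributions often do. Here, though, the protocol states a rule for multiple estimates, so this is more than silence.

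The ROC threshold analysis and the promise in section 16.1 show intent. The first concerns theoretical tools, and neither is tied to the PSA or EVPPI for the actual tools.

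**Conclusion.** The point holds in conditional form. If meta-analysis is not possible, the expected route is expert selection of one study per tool with results in view, and no stated route takes the spread among the other eligible studies into the PSA. Where studies of a tool disagree substantially, decision uncertainty is likely understated and EVPPI for accuracy usually is. Where they agree closely, or the chosen study is small, the single-study figure can be the larger.

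The size cannot be fixed from the documents. The ranges shown rest on assumed study numbers, study sizes, accuracy and between-study SD, and serve only to show direction. This is a cheap improvement worth making before the model is run, not a flaw that invalidates the design.

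**What to change.** Reconcile sections 4.1 and 4.2 by stating what happens when a tool has several eligible accuracy estimates:

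1. Use the expert group to exclude studies on quality and NHS applicability, preferably before accuracy results are shown, and record the reasons.
2. For each tool with two or more eligible studies left, re-run the fully incremental analysis, PSA and EVPPI under each study. Report whether the optimal strategy or the EVPPI ranking changes.
3. Where the data allow pooling, draw sensitivity and specificity jointly from a bivariate random-effects predictive distribution.

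No new data are needed. The cost is some additional modelling time and possibly a less decisive acceptability curve. Step 2 needs no agreed pooling model, so it remains available in the situation section 4.1 anticipates.
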